8.2.5. Skin Pain NRS

Skin Pain NRS will be summarized at each post-baseline visit (Week 1, Week 2, Week 3, Week 4, Week 8, and Week 12). Daily results for each day of Week 1 will also be provided.

In addition, at each post-baseline visit, the change from baseline will be modelled using the same MMRM model used for the analysis of the primary endpoint. LS mean differences between the dupilumab and placebo group, the corresponding 95% CI of the differences and two-sided p-values will be provided. All p-values except for Week 12 will be considered nominal.

8.2.6. Skin Sensitivity to Touch NRS

Skin Sensitivity to Touch NRS will be summarized at each post-baseline visit (Week 1, Week 2, Week 3, Week 4, Week 8, and Week 12).

In addition, at each post-baseline visit, the change from baseline will be modelled using the same MMRM model used for the analysis of the primary endpoint. LS mean differences between the dupilumab and placebo group, the corresponding 95% CI of the differences and two-sided p-values will be provided. All p-values except for Week 12 will be considered nominal.

8.2.7. Skin Burn NRS

Skin Burn NRS will be summarized at each post-baseline visit (Week 1, Week 2, Week 3, Week 4, Week 8, and Week 12).

In addition, at each post-baseline visit, the change from baseline will be modelled using the same MMRM model used for the analysis of the primary endpoint. LS mean differences between the dupilumab and

placebo group, the corresponding 95% CI of the differences and two-sided p-values will be provided. All p-values except for Week 12 will be considered nominal.

8.2.8. Eczema Area Severity Index (EASI)

The EASI total score and percent change from baseline in EASI total score will be summarized at each post-baseline visit. At each post-baseline visit until Week 12, the percent change from baseline in EASI total score will be modelled using the same MMRM model used for the analysis of the primary endpoint. LS mean differences between the dupilumab and placebo group, the corresponding 95% CI of the differences and two-sided p-values will be provided. All p-values except for Week 12 will be considered nominal.

In addition, the responder binary variables EASI50, EASI75 and EASI90 indicating whether the patient achieved at least 50%, 75% and 90% improvement (reduction), respectively, will be summarized and modelled. The number and percentage of patients with EASI50, EASI75 and EASI90 will be presented for each post-baseline visit (Week 1, Week 2, Week 4, Week 8, Week 12, Week 16, Week 20 and Week 24) alongside the number of patients evaluated at that visits. The percentage for each responder variable will be derived based on the number of patients who are evaluable at the visit.

Moreover, at each post-baseline visit until Week 12, the responder variables (EASI50, EASI75 and EASI90) will be modelled using Generalized Linear Mixed Model (GLMM). The terms included will be the same as those in the MMRM model used for the analysis of the primary endpoint. The model will be fitted using PROC GLIMMIX assuming a binomial distribution and logit link. The estimated incidence rate for each treatment group and the corresponding 95% CI of the estimated incidence rates will be provided. The odds ratios and the corresponding 95% CI of the odds ratio with two-sided p-value will be provided. All p-values except for Week 12 will be considered nominal.

The GLIMMIX procedure for modelling the binomial responder variables will be based on the following sample SAS code to evaluate the treatment effect through week 12:

```
proc glimmix data = adcc;
  where paramcd eq "EASI50" and avisitn ge 2 and avisitn le 6 and ITTFL="Y";
  class usubjid stratum avisitn trt01pn(ref='x');
  ** 'x' should be code for the placebo group **
  model resp (event='1') = base trt01pn stratum avisitn avisitn*trt01pn base*avisitn /
    dist=binomial link=logit solution ddfm=kr;
  random _residual_ / subject=usubjid type=UN; ** type can also change here as in mixed
    to TOEPH, TOEP, AR(1) or CS to achieve convergence.**
  lsmeans trt01pn*avisitn / pdiff ilink OR CL;
run;
```

Note that sample code assumes that the relevant post-baseline visits until Week 12 are coded between 2 and 6 inclusive, if that is not the case, the code should be adjusted.

If the GLMM model fails to achieve convergence (even with simpler covariance structures), the responder variables will be analyzed using a logistic regression model, separately at each assessment time point through Week 12. The logistic regression model will include treatment (dupilumab, placebo) as fixed effect, and will include baseline value of EASI, randomization stratum (region) as fixed effect covariates. A summary table will present the estimated incidence for each treatment group and corresponding 95%

confidence interval (CI); also, the odds ratio, corresponding 95% CI and p-value for the treatment difference between the dupilumab and placebo group. An estimate of the odds ratio and a CI above 1 is an indication that you are more likely to be a responder on the active treatment group rather than placebo.

If the logistic regression model fails to achieve convergence at a post-baseline visit, the Clopper Pearson 95% CI of the incidence rate (expressed in percentage) and the 95% CI of the difference in incidence rate between treatment group and placebo (i.e. treatment – placebo) and p-value will be presented. The 95% CI for the difference between dupilumab and placebo will be based on the Cochran-Mantel-Haenszel (CMH) test adjusted by the randomization stratum, at the post-baseline time point.

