8.1.1. Primary Analysis

Percentage change from baseline in sleep quality NRS will be analyzed using a MMRM under the MAR framework. The MMRM model will include treatment (dupilumab, placebo), baseline value of sleep quality NRS, randomization stratum (region), visits (up to week 12), treatment by visit interaction, and baseline sleep quality NRS by visit interaction terms all as fixed effects. An unstructured correlation matrix will be used to model the within -patient errors. The Kenward-Roger approximation (**ddfm=kr**) will be used to estimate the denominator of degrees of freedom. Parameters will be estimated using restricted maximum likelihood method with the Newton-Raphson algorithm. LS mean difference between the dupilumab and placebo group, the corresponding 95% CI of the differences and 2-sided nominal p-values will be provided. The primary p-value is at Week 12. Any other p-values should be treated as suggestive for possible further study as the study is not powered for these tests.

If the number of patients in the PSG-sub study is less than 50% of planned, PSG-strata will be pooled with the non-PSG strata in the US and then there will be only 3 strata: US (combined non-PSG and PSG), Europe and ROW.

If the MMRM model fails to achieve convergence due to complexity of model specification, different covariance structures will be used according to the following order till convergence is achieved:

1. Unstructured correlation (UN)
2. Heterogeneous Toeplitz (TOEPH)
3. Homogeneous Toeplitz (TOEP)
4. First-Order Autoregressive [AR(1)]
5. Compound Symmetry (CS)

MMRM model will be built with the following sample SAS code to evaluate the treatment effect through week 12:

```
proc mixed data = adqs method = reml;
  where paramcd eq 'sleep quality NRS' and avisitn ge 2 and avisitn le 6 and ITTFL eq
  "Y";
  class usubjid stratum trt01pn avisitn;
  model pctchg = base trt01pn stratum avisitn trt01pn*avisitn base*avisitn / solution ddfm
  = kr;
  repeated avisitn / type = un subject = usubjid;
  lsmeans trt01pn*avisitn / cl;
  /*contrast "Dupilumab vs Placebo at Week 1 Visit 2"
    trt01pn -1 1 trt01pn*avisitn -1 0 0 0 0 1 0 0 0 0;
  contrast "Dupilumab vs Placebo at Week 2 Visit 3"
    trt01pn -1 1 trt01pn*avisitn 0 -1 0 0 0 0 1 0 0 0;
  contrast "Dupilumab vs Placebo at Week 4 Visit 4"
    trt01pn -1 1 trt01pn*avisitn 0 0 -1 0 0 0 0 1 0 0;
  contrast "Dupilumab vs Placebo at Week 8 Visit 5"
    trt01pn -1 1 trt01pn*avisitn 0 0 0 -1 0 0 0 0 1 0; */

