15.3.3. Handling of missing data for Clinician Reported Outcomes (CLINROS)

No imputation will be made for missing or incomplete data.

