15.5. Visit Windows

The following steps will decide how the scheduled and/or unscheduled visits will be used in the analyses on efficacy variables and the by-visit summaries for safety variables.

Step 1: A scheduled measurement (described in [Appendix 15.2](#)) will be used if it is available; otherwise, an unscheduled measurement (including the end of treatment/study visit for those prematurely discontinued) will be used if it happens to be on the same date as the date of the scheduled visit.

Step 2: After Step 1, if there is still no measurement for a given parameter at a scheduled visit, the analysis window below “[in brackets]” will be applied to re-allocate a post-baseline unscheduled measurement to a scheduled measurement.

Table 15.5.1 Analyses window definition

Scheduled visit post baseline	Targeted study day	Analysis window			
		PSG	Weight	PVT, ANAM, ACQ-5 and AR-VAS	All other endpoints/parameters
Week 1 (Visit 2)	7				[1, 11]
Week 2 (Visit 3)	14				[12, 21]
Week 4 (Visit 4)	28				[22, 42]
Week 8 (Visit 5)	56				[43, 70]
Week 12 (Visit 6)	84	[1,~]		[1, 126]	>=71 for patients who did not enter OLE. [71, 1st dose date of OLE[for patients entered OLE.
Week 16 (Visit 7)	112				[First dose of OLE, 126]
Week 20 (Visit 8)	140				[127, 154]

Scheduled visit post baseline	Targeted study day	Analysis window		
		PSG	Weight	PVT, ANAM, ACQ-5 and AR-VAS
Week 24 (Visit 9)	168		[1,~]	[127,~]
				All other endpoints/parameters [155, ~]

Study days are calculated from the day of first administration of IMP; the day of first administration of IMP (or the day of randomization if not exposed) is Day 1.

For endpoints with daily assessments until Week 4, Week 3 will be summarized. Week 3 visit is assigned to records which lie on the 7 days following the final day of Week 2. If this 7 day window overlaps with already assigned Week 4 records then Week 3 will have a duration of less than 7 days.

After applying the above time windows, if multiple assessments are associated to the same time point, the closest from the targeted study day will be used. In case of equality, the last measurement will be used. Re-allocated scheduled visits (i.e., visit numbers) should be sequential if ordered by the date of measurement.

After Step 2, if there is still no measurement for a given parameter at a scheduled visit, data is considered missing.

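### The sample GLIMMIX code for EASI50/75/90 does not name the visit in its residual covariance, so a skipped visit with no retained record can put later visits into the wrong covariance rows

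*SAP*

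**What the plan says.** SAP 8.2.8 models the three responder variables over the five visits from Week 1 to Week 12 (Weeks 1, 2, 4, 8 and 12). On the model terms it says: "The terms included will be the same as those in the MMRM model used for the analysis of the primary endpoint". The text does not describe the residual covariance. That appears only in the sample code, as "random _residual_ / subject=usubjid type=UN", with a comment that the "type can also change here as in mixed" through the same list of simpler structures (TOEPH, TOEP, AR(1), CS). The corresponding line of the primary model in SAP 8.1.1 is "repeated avisitn / type = un subject = usubjid".

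On gaps in the EASI data:

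- SAP 15.5, after the visit windows are applied: "After Step 2, if there is still no measurement for a given parameter at a scheduled visit, data is considered missing".
- SAP 15.3.3, for clinician-reported outcomes: "No imputation will be made for missing or incomplete data".
- SAP 8.2.8, on the denominator: "The percentage for each responder variable will be derived based on the number of patients who are evaluable at the visit".
- SAP 15.3.1 counts a patient as a non-responder only at time points after discontinuation, or after the start of rescue or selected prohibited medication. It also sets off-treatment values to missing during a Covid-19 interruption and uses the values collected after treatment resumes.
- SAP 15.1 says something different for binary secondary endpoints. Its table lists the Cochran-Mantel-Haenszel test with missing values counted as non-response.

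**The concern.** A covariance matrix across visits is meaningful only if each record is tied to its visit. The MMRM line does this through `avisitn`. The GLIMMIX line gives only the patient and the structure, so the one index left is the order of the records within the patient. For a patient with all five visits, order and visit coincide. For a patient with a gap followed by a later visit they do not, and variances and correlations from different visits are estimated as if they were the same quantity.

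The estimated treatment effects depend on that matrix through the weighting, so the Week 12 odds ratio, its confidence interval and its p-value can all move. EASI50 and EASI75 at Week 12 are secondary endpoints in protocol section 3, and the SAP adds EASI90. Their reported figures should not depend on whether a dataset happens to hold a row for a missed visit.

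**Working it through.** The documents give no response rate, odds ratio or power for the EASI responder endpoints, so there is no stated figure to reproduce. The check has two parts.

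**1. Row assignment.** With five visits the unstructured matrix has 5 × 6 / 2 = 15 parameters.

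| Row | Patient with all visits | Patient without Week 2, no record kept |
|---|---|---|
| 1 | Week 1 | Week 1 |
| 2 | Week 2 | Week 4 |
| 3 | Week 4 | Week 8 |
| 4 | Week 8 | Week 12 |
| 5 | Week 12 | (empty) |

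Week 12 of the second patient shares a row with Week 8 of the first. With the latent correlation assumed in part 2, 0.35 + 0.65 × exp(−lag in weeks / 4), rows 1 and 2 mean:

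- complete patient, Weeks 1 and 2: 0.35 + 0.65 × exp(−1/4) = 0.86
- patient with the gap, Weeks 1 and 4: 0.35 + 0.65 × exp(−3/4) = 0.66

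The two are forced to share one parameter. Under compound symmetry all variances are equal and all correlations are equal, so row position has no effect. If a patient drops out and does not return, the visits present are still rows 1, 2, 3 and so on, so nothing moves.

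**2. Size, by simulation.** From the SAP: 201 patients, 2:1 allocation, five visits, and fixed effects for baseline, treatment, stratum, visit, treatment by visit and baseline by visit. Assumed, not in the documents:

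- response rates of 15/32/50/65/70% on dupilumab and 5/15/25/38/45% on placebo
- the correlation above
- visits at Weeks 1 to 8 skipped at random, at the same rate in both arms, with Week 12 always observed.

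Each simulated trial was fitted twice with a marginal logit pseudo-likelihood model and unstructured covariance, once with rows placed by visit and once by record order. This was coded in Python, not SAS, with normal-theory p-values rather than Kenward-Roger.

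The expected share of patients with shifted rows is 1 − (1 − skip rate)^4: 3.9%, 7.8%, 18.5% and 34.4% at skip rates of 1%, 2%, 5% and 10%. The simulated shares agree.

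| Skipped per visit | Trials fitted | Patients shifted | OR factor: median | 95th percentile | Maximum | Mean change in log OR | SE ratio, range | Significance changed |
|---|---|---|---|---|---|---|---|---|
| 1% | 119 | 4.0% | 1.006 | 1.02 | 1.03 | +0.002 | 0.98–1.01 | 0 |
| 2% | 119 | 7.7% | 1.011 | 1.03 | 1.04 | +0.004 | 0.98–1.01 | 1 |
| 5% | 118 | 18.1% | 1.015 | 1.05 | 1.10 | +0.005 | 0.97–1.02 | 0 |
| 10% | 118 | 33.8% | 1.027 | 1.08 | 1.12 | +0.008 | 0.97–1.03 | 2 |

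The OR factor is the ratio of the two Week 12 odds ratios, taken as 1 or more whichever is larger. At 10% skipped, the median odds ratio with rows placed by visit is 2.90. A median shift takes it to 2.90 × 1.027 = 2.98 or 2.90 / 1.027 = 2.82. The signed mean change (0.008) is well below the median absolute change (ln 1.027 = 0.027), so shifts go both ways.

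Three control settings gave identical fits: no skipped visits, dropout-only missingness, and 5% skipped under compound symmetry. TOEPH, TOEP and AR(1) also depend on row position but were not simulated.

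**The case against.** The strongest reply is that this is sample code whose intent is clear. The section says the responder model mirrors the MMRM, and a competent programmer would probably name the visit. The SAP also speaks of values being set to missing, not of records being deleted, and a placeholder record with a missing response might keep the positions. Both points lower the chance of harm. Neither removes the fault: this line is the only specification of the covariance, and the SAP requires no placeholder record.

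Second, the gaps may be few. Unscheduled measurements are reallocated through contiguous windows (Days 22 to 42 for Week 4), so a gap needs no usable value in the whole window. SAP 8.1.7 expects few Covid-19 treatment interruptions, and discontinued or rescued patients are counted as non-responders. This stands, and it makes the lower skip rates in the table more plausible than the higher ones. But SAP 5.1 plans a table of visits not done because of Covid-19, so gaps are foreseen.

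Third, if the rule in SAP 15.1 applied to this model, every gap would be filled and the problem would vanish. However, 8.2.8 and 15.3.3 point the other way, and SAP 13 makes Cochran-Mantel-Haenszel the last fallback, so the entry in 15.1 may not have been updated.

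A reader might infer that the EASI results would be biased, that the type I error would be inflated, or that any missing EASI value would change the odds ratio. The working does not support these readings. The mean change was at most 0.008 on the log scale, and trailing dropout had no effect. The runs assumed a treatment effect, so they do not measure type I error directly, but nothing in them suggests inflation.

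**Conclusion.** The code line is wrong as written, but its effect is conditional and usually small. It needs an intermittent gap, no retained record, no non-responder fill, and convergence under UN or another structure that depends on row position. Under those conditions the reported Week 12 odds ratio typically shifts by 1% to 3%, and occasionally by about 10%. Significance at 0.05 changed in 3 of 474 simulated trials (0.6%). These sizes rest on the assumed response rates, correlation and skip rates; the misassignment of rows does not.

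The consequence is confined to the reported EASI50/75/90 figures. SAP 8.2.23 orders eight key secondary endpoints, none of them an EASI responder endpoint, and reports the others at nominal level. A reader should not conclude that the primary analysis or the hierarchy is at risk. This is a minor coding correction worth making because it is free.

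**What to change.** In SAP 8.2.8, replace the residual statement with

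`random avisitn / subject=usubjid type=un residual;`

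and use the same form, changing only the type, for TOEPH, TOEP, AR(1) and CS. This keeps the same covariance structures and numbers of parameters, and matches the MMRM code. It costs one line of sample code, with no effect on data collection, sample size or error rate.

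Separately, reconcile the binary-endpoint row of SAP 15.1 with 8.2.8 and 15.3, so that one rule states whether a skipped EASI visit is left missing or counted as non-response. That choice changes what the responder proportions mean and should be made before database lock. If gaps are left missing, the corrected line is needed; if they are filled, it does no harm.

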8.2.9. Patient oriented eczema measure (POEM)

The POEM total score will be summarized at each post-baseline visit (Week 4, Week 12, and Week 24).

In addition, at each post-baseline visit until Week 12, the change from baseline will be modelled using the same MMRM model used for the analysis of the primary endpoint. LS mean differences between the dupilumab and placebo group, the corresponding 95% CI of the differences and two-sided p-values will be provided. All p-values except for Week 12 will be considered nominal.

Change from baseline to Week 24 and Change from Week 12 to Week 24 will be summarized on the OLE analysis set using descriptive statistics in each treatment group (those originally randomized to in the double-blind study treatment period). No comparative statistical analyses will be done.

8.2.10. PROMIS Sleep Related Impairment Short Form 8a

The PROMIS Sleep Related Impairment SF8a total raw and T-scores will be summarized at each post-baseline visit (Week 1, Week 2, Week 4, Week 8, Week 12, Week 16, Week 20, and Week 24). T-score calculation is defined in [Table 15.8.1](#).

In addition, at each post-baseline visit until Week 12, the change from baseline for raw score and T-score will be modelled using the same MMRM model used for the analysis of the primary endpoint. LS mean differences between the dupilumab and placebo group, the corresponding 95% CI of the differences and two-sided p-values will be provided. All p-values except for Week 12 will be considered nominal.

Change from baseline to Week 24 and Change from Week 12 to Week 24 will be summarized on the OLE analysis set using descriptive statistics in each treatment group (those originally randomized to in the double-blind study treatment period). No comparative statistical analyses will be done.

8.2.11. Epworth Sleepiness Scale (ESS)

The ESS will be summarized at each post-baseline visit (Week 4, Week 12, and Week 24).

In addition, at each post-baseline visit, the change from baseline will be modelled using the same MMRM model used for the analysis of the primary endpoint. LS mean differences between the dupilumab and placebo group, the corresponding 95% CI of the differences and two-sided p-values will be provided. All p-values except for Week 12 will be considered nominal.

8.2.12. Dermatology Life Quality Index (DLQI)

The DLQI will be summarized at each post-baseline visit (Week 4, Week 12, and Week 24).

In addition, at each post-baseline visit until Week 12, the change from baseline will be modelled using the same MMRM model used for the analysis of the primary endpoint. LS mean differences between the

dupilumab and placebo group, the corresponding 95% CI of the differences and two-sided p-values will be provided. All p-values except for Week 12 will be considered nominal.

Change from baseline to Week 24 and Change from Week 12 to Week 24 will be summarized on the OLE analysis set using descriptive statistics in each treatment group (those originally randomized to in the double-blind study treatment period). No comparative statistical analyses will be done.

8.2.13. SCORing of Atopic Dermatitis (SCORAD)

The SCORAD total score and sleep VAS will be summarized at each post baseline visit (Week 1, Week 2, Week 4, Week 8, Week 12, Week 16, Week 20, and Week 24).

In addition, at each post-baseline visit until Week 12, the change from baseline will be modelled using the same MMRM model used for the analysis of the primary endpoint. LS mean differences between the dupilumab and placebo group, the corresponding 95% CI of the differences and two-sided p-values will be provided. All p-values except for Week 12 will be considered nominal.

Change from baseline to Week 24 and Change from Week 12 to Week 24 will be summarized on the OLE analysis set using descriptive statistics in each treatment group (those originally randomized to in the double-blind study treatment period). No comparative statistical analyses will be done.

8.2.14. Juniper Asthma Control Questionnaire (ACQ-5)

The ACQ-5 global score will be summarized at each post-baseline visit (Week 12 and Week 24).

In addition, the change from baseline at Week 12 will be modelled using the same MMRM model used for the analysis of the primary endpoint. LS mean difference between the dupilumab and placebo group, the corresponding 95% CI of the difference and two-sided p-value will be provided. All p-values except for Week 12 will be considered nominal.

